### Inclusion of Women, Minorities, and Children

Racial and ethnic minority patients were represented in the VA National Patient Care Database and other VA datasets. 2017 estimates were that 11% of the VHA population was Black, 6% were Hispanic/Latino, and 4% were of another minority group. At 8%, women constitute a minority of the VHA population. However, this number is increasing, and all women Veterans who met inclusion criteria were included in this study. No children were included in this study.

## 5.2 EXCLUSION CRITERIA

The RaPPID Program avoided de-prescribing PPIs in patients for whom chronic PPI therapy was recommended by guidelines, consensus statements, and/or expert opinion. Stopping PPIs in these patients could have caused harms such as upper GI bleeding. Patients taking PPIs were excluded from the dashboard if they had one or more of the characteristics listed in the table below.

Twice-daily PPI Users with Zollinger-Ellison	
Once-daily PPI Users with any the following characteristics:	

■ Eosinophilic esophagitis

■ Esophagitis

■ Barrett's esophagus

■ Peptic ulcer

■ Zollinger-Ellison

■ Idiopathic pulmonary fibrosis

	

■ Pancreatic enzyme replacement

■ Esophageal ulcer

■ Esophageal stenosis/stricture

■ Dysphagia (other than oropharyngeal)

OR	
NSAID Users Meeting any of the following criteria:	Low-dose Aspirin Users Meeting any of the following criteria:

■ age > 65 years of age

■ Take a 2nd NSAID

■ Take daily aspirin

■ Take an anti-thrombotic drug

■ Take an oral steroid

	

■ age <math>\geq</math> 60 years of age

■ Take NSAIDs regularly

■ Take an anti-thrombotic drug

■ Take a corticosteroid

## 6 EXPERIMENTAL MANIPULATIONS

### 6.1 EXPERIMENT

Experiment: Behavioral	
Intervention Arm PPI De-prescribing Program	Control Arm Usual Care/No PPI De-prescribing Program

■ Alerts to clinical pharmacy specialists and primary care providers informing them of individual patients scheduled for upcoming primary care visits who meet criteria for PPI de-prescription

■ Activation of clinical pharmacy specialists

■ Education of primary care providers

■ Patient Education

	

■ Usual Care

■ Did not receive the national de-prescribing program

The study focused on the effect of the operational intervention, RaPPID, as compared to usual care. See Section 4.1.1 for detailed descriptions of intervention components.

## 6.2 MEASURES TO MINIMIZE BIAS: RANDOMIZATION AND BLINDING

Randomization of VISNs (regions) was done by the study biostatistician. The investigators and operational partners were informed of the assignments after randomization was finalized.

There was no blinding once randomization was complete.

## 6.3 PARTICIPANT WITHDRAWAL FROM THE STUDY & LOST TO FOLLOW-UP

Not applicable for RCT as all subjects electronically enrolled were analyzed.

For patient reported outcomes, we expected some missing data. Our initial analyses only used observed data, but for missing data for items within scales, we used recommended imputation strategies. For missing 3-month survey assessments, we used logistic regression with missing follow-up as a dependent variable to see if missingness is associated with baseline variables, including facility-level variables. We included baseline variables found to be predictive of missingness in the longitudinal data model, and if missingness was at random, longitudinal mixed-effects provided an unbiased estimate of the study group effect. If the extent of missingness is more than 20%, we conducted a secondary analysis by combining results based on multiply imputed data using sequential regression multivariate imputation method,

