### 7.2.1 VARIABLES & DATA SOURCES

Variable	Description	Time Frame	Data Source
Primary Outcome			
PPI de-prescribing	Proportion of days PPI prescribed after index visit ( H1 )	12 mo	CDW
Secondary Outcomes			
Utilization of outpatient care	Outpatient visit, ED visit, or upper endoscopy (EGD) for: (1) upper GI symptoms/conditions; (2) any cause	12 mo	CDW
Utilization of inpatient care	Hospital admission for: (1) upper GI symptoms/conditions; (2) any cause	12 mo	CDW
Serious GI complications	Complications of peptic ulcer disease (bleeding, obstruction, perforation)	12 mo	CDW
PPI-related harms	E.g., fractures, enteric infections, pneumonia, kidney disease, dementia	12 mo	CDW
Upper GI symptoms	Upper GI symptoms (RDQ)	0, 3 mo	Surveys
Cost	Healthcare expenditures related to VA and non-VA care	24 mo	Calculated
Reach	Proportion of patients offered de-prescribing	3 mo	Post Survey
Adoption	Reduction in PPI use before / after program deployment	3, 12 mo	CDW
Implementation	Implementation fidelity and consistency at each site (process)	3, 12 mo	Staff Interviews

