#### 8.1.2 VETERAN SURVEYS

Recruitment numbers were based on a power calculation in which patient-reported symptoms, as measured by the Reflux Disease Questionnaire, were treated as a continuous variable rather. Based on previous research, we assumed an RDQ score Standard Deviation (SD)=1.3 for GERD patients for this calculation. To detect the between-group difference of 0.71 vs. 1.13, assuming SD=1.3 with 90% power and alpha=0.01, we need 287 surveys completed per group (574 in total) at 3 months and 820 in total surveys returned at baseline to account for 30% dropout by month 3. We estimated a 50% response rate for the baseline survey and a 70% response rate for the follow-up survey. we mailed 1,722 baseline surveys and approximately 850 follow-up (3 month) surveys.

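### Missing 3-month symptom surveys: Section 6.3 names only baseline predictors and plans no departure from missing-at-random, although post-visit VA prescribing and utilization records exist for non-responders

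*Combined protocol and SAP*

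**What the plan says.** Section 8 states H3: upper GI symptoms are to be non-inferior under the intervention. Section 8.3 judges this on the 3-month RDQ score, by setting the effect estimate and its 90% confidence interval against a margin whose value is not given.

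Section 6.3 deals with missing surveys in three steps:

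- Observed data are analyzed first, with imputation only for items within scales.
- Missing 3-month surveys are examined by logistic regression "with missing follow-up as a dependent variable to see if missingness is associated with baseline variables, including facility-level variables". Baseline variables that predict missingness enter the longitudinal mixed model, which is described as unbiased under missing-at-random.
- "If the extent of missingness is more than 20%, we conducted a secondary analysis", using multiple imputation by sequential regression. The imputation variables are not named. The extracted sentence ends at a comma, so some text may have been lost.

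Section 8.1.2 plans for "820 in total surveys returned at baseline to account for 30% dropout by month 3", and says the same in terms of response: "We estimated a 50% response rate for the baseline survey and a 70% response rate for the follow-up survey".

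Section 7.2.1 gives CDW as the source for post-visit PPI prescribing and for "Outpatient visit, ED visit, or upper endoscopy (EGD) for: (1) upper GI symptoms/conditions; (2) any cause". Section 8.3, on the primary outcome, notes that this collection is electronic and asks nothing more of the patient. Section 7.2.2 sets the limit: heartburn medicines bought over the counter or obtained outside VA are among the reasons for using surveys at all.

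**The concern.** The RDQ is measured at 0 and 3 months only (Section 7.2.1). A patient who does not return the second survey therefore gives the mixed model nothing but pre-visit information. Much of what could drive both symptoms and survey return at month 3 happens after the visit: VA PPI stopped, continued or resumed, or a visit for upper GI complaints. The program exists to make PPI status differ by arm, assignment was not blinded (Section 6.2), and the surveyed intervention VISN was the one with the most Dashboard activity (Section 7.2.2). Missing-at-random given baseline variables alone is hard to defend in that setting.

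At stake is the H3 estimate. The RDQ is the trial's only direct symptom scale, and understated harm works in favour of a non-inferiority claim, so the missing-data assumption deserves a stress test that Section 6.3 does not plan.

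**Working it through.** **The plan's own figures.** Section 8.1.2 sizes the survey "To detect the between-group difference of 0.71 vs. 1.13", "assuming SD=1.3 with 90% power and alpha=0.01".

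- Difference: 1.13 − 0.71 = 0.42.
- Normal approximation, two-sided alpha 0.01: n = 2 × 1.3² × (2.576 + 1.282)² / 0.42² ≈ 285.1, so 286 per group. The t-based calculation gives 287, which matches "we need 287 surveys completed per group (574 in total) at 3 months". A one-sided alpha would give 250 and does not match.
- Loss: 574 / 0.70 = 820, as stated. Since 30% exceeds 20%, the imputation trigger is expected to be met.

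**Precision.** With 287 per arm, ignoring clustering and covariates, SE = 1.3 × √(2/287) = 0.109. The 90% half-width is 1.645 × 0.109 ≈ 0.179.

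**Bias from baseline-only handling.** Suppose 3-month response depends on post-visit PPI status. Let p be the share off PPI in an arm, r_off and r_on the response rates, and d the RDQ increase from being off PPI. The share off PPI among responders is

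f = p·r_off / (p·r_off + (1 − p)·r_on),

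and the bias in the intervention-minus-control difference is

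d × [(f_I − f_C) − (p_I − p_C)].

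The documents give none of these inputs, so all are assumptions: p_I = 0.50 and p_C = 0.25 (borrowed from the 75% versus 50% of days on PPI in Section 8.1.1), and d from 0.42 to 1.3 (the design difference up to one SD). The work is on the RDQ point scale of Section 8.1.2.

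| Response off / on PPI | f_I | f_C | Bracket | Bias, d = 0.42 | Bias, d = 1.3 |
|---|---|---|---|---|---|
| (a) 60% / 80% in both arms | 0.30/0.70 = 0.429 | 0.15/0.75 = 0.200 | −0.021 | −0.009 | −0.028 |
| (b) 60% / 80% intervention only; control 70% | 0.429 | 0.250 | −0.071 | −0.030 | −0.093 |
| (c) 50% / 90% intervention only; control 70% | 0.25/0.70 = 0.357 | 0.250 | −0.143 | −0.060 | −0.186 |

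Negative values favour non-inferiority. A steeper pattern common to both arms (50% / 82%) gives −0.017 to −0.052. Reversing the response pattern in (b) or (c) gives the same size with a positive sign. The extreme of (c) is 0.186 / 0.42 = 44% of the design difference and about one 90% half-width.

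**Would CDW variables help?** A simulation of case (c) with d = 1.3 (410 per arm, 400 runs, assumed baseline-to-outcome correlation 0.5) gave these biases:

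- mixed-model analogue on baseline covariates: −0.190;
- multiple imputation on baseline variables only: −0.191, so no gain;
- multiple imputation adding correct CDW status and its interaction with arm: −0.007, close to zero given a Monte Carlo error of about 0.106/√400 = 0.005;
- the same, with 20% or 40% of true PPI users appearing off PPI in CDW through over-the-counter or non-VA supply: −0.072 or −0.128.

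**The case against.** The case against is substantial, and most of it limits how far the point can go.

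- A reader might infer that the whole missing-data plan, imputation included, uses baseline variables only. That is certain for the non-response model and the longitudinal model. The imputation variables are unstated, and the sentence may be truncated by extraction.
- A reader might infer that CDW shows whether each non-responder stopped or resumed PPI. It shows VA prescribing. Over-the-counter and non-VA use is collected in the returned survey (Section 7.2.2), so it is unknown for non-responders. H2RA prescribing is not in the Section 7.2.1 table.
- A reader might think CDW could test missing-at-random. It can show whether non-response depends on recorded VA prescribing. Once that record is conditioned on, the remaining assumption cannot be tested, which is why a sensitivity analysis is still needed.
- A reader might conclude that H3 would be declared too easily. Patients doing badly may return more surveys rather than fewer, and the bias then reverses. The 0.42 is a sizing difference and not a margin, so no reversal of the conclusion can be demonstrated.
- A reader might multiply the 30% loss by an assumed shift, for example 0.30 × 1.4 = 0.42, and report the full design difference as bias. That shift exceeds one SD and is placed in one arm only. It describes a tipping-point scale, not the bias from leaving out CDW data.
- Making imputation the main analysis would gain nothing by itself, as the simulation shows. CDW utilization for upper GI symptoms and the repeated SF-12 also give evidence that bears on H3.

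What stands after this: no post-visit variable is named for the missing-data work, no departure from missing-at-random is planned, and relevant records are already held for non-responders.

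**Conclusion.** The point holds as a worthwhile, cheap improvement. Section 6.3 conditions its non-response check and longitudinal model on baseline variables, leaves the imputation model unspecified, and plans nothing for data missing not at random, while expecting 30% loss on a non-inferiority outcome.

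The size depends on unknown response behaviour. If response depends on PPI status alike in both arms, the bias is about 0.01 to 0.03 RDQ points under the 60% / 80% pattern and about 0.05 at most under the steeper one tried. If the dependence is strong and confined to one arm, it reaches about 0.19. Response rates by PPI status, shares off PPI, the off-PPI effect, the misclassification rates and the correlation are all assumed. Neither the direction of bias nor a changed H3 conclusion can be established from the documents.

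**What to change.** In Section 6.3:

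- Add post-index CDW variables up to month 3 to the non-response check: VA PPI prescribed at or above the baseline frequency, PPI resumption, upper GI visit or endoscopy, and VA H2RA prescription if it is extracted.
- Name the same variables, by arm, in the multiple imputation that the expected loss will trigger. The imputation may remain secondary.
- Add a delta (tipping-point) analysis that shifts imputed intervention-arm RDQ values upward until non-inferiority is lost, and report that shift. This requires the margin value to be stated.

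Parts of the document are written as a final report. If H3 has already been analyzed, present these as labelled supplementary analyses.

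The cost is analysis time, some extra data extraction, and possibly a wider interval or a less favourable statement on H3. Over-the-counter and non-VA use will leave some bias that CDW variables cannot remove.

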# 7 PROCEDURES AND STUDY ASSESSMENTS

## 7.1 PROCEDURES

It was recommended that patients meeting inclusion-exclusion criteria should be deprescribed using one of the methods below. Some patients with GERD were expected to have recurrence of frequent bothersome symptoms intermittently in the coming months or years. Studies have suggested such patients can be well-managed by intermittent courses of once-daily PPI for up to 4 weeks. On-demand PPI therapy (in which the patient takes PPIs as they determine is needed based on symptoms and response) was also shown to be well accepted by patients with GERD. Only a minority of GERD patients should require daily maintenance PPI therapy to provide acceptable symptom relief. The table below was part of the educational materials for Pharmacy and Primary Care providers.

Patients Taking PPIs	
Once Daily	Twice Daily

▪ Taper to every other day for 2 weeks and then discontinue

▪ Prescribe H2-receptor antagonists (e.g., famotidine, ranitidine) to take as needed for intermittent recurrent symptoms

	

▪ Taper to once daily PPI, taken 30-60 minutes before a meal

Patients should be cautioned that they may have rebound symptoms for a few weeks after discontinuation.	

## 7.2 DATA COLLECTION

Data was collected from several sources, including: (1) VHA Corporate Data Warehouse (CDW); (2) surveys of Veterans; and (3) semi-structured interviews with CPS providers, GI providers, and PCPs as part of the process evaluation. Key measures are shown the table below.

### 7.2.1 VARIABLES & DATA SOURCES

Variable	Description	Time Frame	Data Source
Primary Outcome			
PPI de-prescribing	Proportion of days PPI prescribed after index visit ( H1 )	12 mo	CDW
Secondary Outcomes			
Utilization of outpatient care	Outpatient visit, ED visit, or upper endoscopy (EGD) for: (1) upper GI symptoms/conditions; (2) any cause	12 mo	CDW
Utilization of inpatient care	Hospital admission for: (1) upper GI symptoms/conditions; (2) any cause	12 mo	CDW
Serious GI complications	Complications of peptic ulcer disease (bleeding, obstruction, perforation)	12 mo	CDW
PPI-related harms	E.g., fractures, enteric infections, pneumonia, kidney disease, dementia	12 mo	CDW
Upper GI symptoms	Upper GI symptoms (RDQ)	0, 3 mo	Surveys
Cost	Healthcare expenditures related to VA and non-VA care	24 mo	Calculated
Reach	Proportion of patients offered de-prescribing	3 mo	Post Survey
Adoption	Reduction in PPI use before / after program deployment	3, 12 mo	CDW
Implementation	Implementation fidelity and consistency at each site (process)	3, 12 mo	Staff Interviews

### 7.2.2 STUDY ASSESSMENTS - VETERAN SURVEYS

One potential unintended consequence of PPI de-prescription is worsening upper GI symptoms. Worsening symptoms can substantially affect quality of life and promote use of medications and healthcare resources. Importantly, these medications and healthcare resources need not be sought within VA. For example, medications to alleviate heartburn may be obtained over-the-counter (OTC) or from a non-VA provider. Therefore, we used surveys to assess and track outcomes that could not be measured electronically, including upper GI symptoms, quality of life, and use of non-VA healthcare resources. We developed two surveys with distinct elements: (1) a pre-visit survey, to be completed 1-2 weeks prior to the index primary care visit; and (2) a post-visit survey, to be completed 3 months after the index primary care visit. Surveys were administered to subjects in the VISN with the most Dashboard activity (a high participation VISN) and a comparable control VISN.

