## 1.2 SCHEMA

Months 1-11

Validate PPI Dashboard Algorithm & Test User Interface  
Develop Educational Materials

Randomize

Intervention  
N = 9 VISNs

Control  
N = 8 VISNs

Month 12

Activate VISN Pharmacy Executives, Clinical Pharmacy Specialists & Academic Detailers  
Make Dashboard Available to Intervention Sites

Months 12-24

Electronically Enroll Patients in Dashboard  
Send Baseline Surveys to Patients of 2 VISNs (1 from each arm)

Months 15-27

Send 3-Month Follow-up Surveys to Patients of 2 VISNs (1 from each arm)

Months 24-36

12-month Follow-up of Enrolled Patients

Months 36-42

Data Analyses

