**Covariates:** Covariates included demographics (age, sex, race/ethnicity), Charlson comorbidity index, indication for PPI use (uncomplicated GERD vs no indication), and baseline PPI dosing frequency (once-daily vs twice-daily). We also collected covariates on a subset of patients (1 intervention VISN and 1 control VISN), using our survey questionnaires, including baseline RDQ symptom score, trust in provider, baseline concern about PPI harms, and receptiveness to de-prescribing of PPIs.

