#### 8.1.1 PRIMARY OUTCOME

Assuming approximately the same number of eligible subjects in each VISN (with an average of 10,563 candidates per VISN) and an ICC of 0.12, randomizing 17 VISNs will give more than 80% power to detect % days on PPI of 75% vs. 50%, 85% vs. 60%, 80% vs. 55%, or 70% vs. 45%, but to detect a difference between 70% vs. 50%, power is only 61% using 0.05 level 2-sided test.

[figure not shown]

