### 8.1.3 FINAL REPORT UPDATE: RCT CONSORT DIAGRAM

8.1.4 FINAL REPORT UPDATE: SURVEYS CONSORT DIAGRAM

## 8.2 POPULATIONS FOR ANALYSES

- Intention-to-Treat (ITT) Analysis Population
- Repeated Measures
  - In addition to intent-to-treat, patient reported outcomes will be measured through surveys over time.

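### The symptom outcome (H3) was surveyed in one VISN per arm of a VISN-randomized trial, so its planned clustering adjustment cannot be estimated and its sample size assumes no between-VISN variation

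*Combined protocol and SAP*

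**What the plan says.** Section 6.2 makes the VISN the unit of randomization: "Randomization of VISNs (regions) was done by the study biostatistician". The schema in section 1.2 shows 9 intervention and 8 control VISNs.

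The symptom surveys were confined to one VISN per arm. Section 7.2.2 says: "Surveys were administered to subjects in the VISN with the most Dashboard activity (a high participation VISN) and a comparable control VISN". The schema and the covariates paragraph of section 8 give the same two-VISN restriction.

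The analysis text covers H3 in three places:

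- Section 8.3 puts outpatient utilization (H2) and symptoms (H3) under generalized linear mixed models with a logit link, allowing for VISN clustering and the randomization strata. The RDQ at 3 months is the outcome, and a 90% CI is compared with a non-inferiority margin that is not given a value.
- Section 6.3 describes a longitudinal model for the surveys: "if missingness was at random, longitudinal mixed-effects provided an unbiased estimate of the study group effect".
- Section 8.2 lists repeated measures as well: "In addition to intent-to-treat, patient reported outcomes will be measured through surveys over time".

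The two sample size sections treat clustering differently. Section 8.1.1 allows for it in the primary outcome: "an ICC of 0.12, randomizing 17 VISNs will give more than 80% power". Section 8.1.2 sizes H3 from a difference (0.71 against 1.13), an SD of 1.3, alpha 0.01, 90% power and 30% dropout, with no ICC or design effect.

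**The concern.** When clusters are randomized, the error for the arm comparison must include variation between clusters. With one VISN per arm, any difference between the two VISNs that has nothing to do with the programme cannot be told apart from a programme effect. The model in section 8.3 cannot supply the missing error term, so the interval that can be computed is in effect an unclustered one.

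This matters because section 8 states the overall hypothesis as less PPI use without a clinically meaningful rise in upper GI symptoms or complications, and H3 is one of its two stated non-inferiority hypotheses. Section 7.2.2 says the surveys were used because symptoms could not be measured electronically. In a non-inferiority comparison, an interval that is too narrow makes false reassurance about a harm more likely. Nothing in the plan limits H3 to a statement about two VISNs.

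**Working it through.** **Degrees of freedom.** H3 has 2 VISNs and 2 arm means, so 2 − 2 = 0 between-VISN degrees of freedom. The VISN variance cannot be separated from arm. If the two VISNs share a stratum, the strata term is constant. If they do not, it coincides with arm. Either way it cannot be estimated. This step needs no assumed ICC.

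**The plan's own figure (section 8.1.2).** Inputs: difference 1.13 − 0.71 = 0.42, SD 1.3, alpha 0.01, power 0.90. The sidedness of alpha is not stated.

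- A two-sided t-test for independent patients needs 286.8 per group, which rounds up to the stated 287.
- A one-sided test needs 250.8, which does not match.
- Dropout: 2 × 287 = 574, and 574/0.70 = 820, as stated.

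The arithmetic is right, with the between-VISN variance set to zero.

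**Effect of between-VISN variation.** The ICC values 0.001 and 0.01 are assumptions, because the documents give none for RDQ. The 0.12 in section 8.1.1 is for prescribing and is not carried over. With one VISN per arm and n = 287:

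- SE = √{2 × 1.69 × [ICC + (1 − ICC)/287]}
- SE_within = √{2 × 1.69 × (1 − ICC)/287}
- SD of the chance difference between two VISNs = 1.3 × √(2 × ICC)
- Power to detect 0.42, with VISN variance treated as known = Φ(0.42/SE − 2.576)
- 90% CI half-width including VISN variance = 1.645 × SE
- One-sided error at the margin if VISN is ignored = Φ(−1.645 × SE_within/SE)

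| ICC (assumed) | SE | SD of chance VISN difference (share of 0.42) | Power for 0.42 | 90% half-width | One-sided error, VISN ignored |
|---|---|---|---|---|---|
| 0 | 0.109 | 0 | 90% | 0.18 | 5.0% |
| 0.001 | 0.123 | 0.058 (14%) | 80% | 0.20 | 7.4% |
| 0.01 | 0.213 | 0.184 (44%) | 27% | 0.35 | 20.2% |

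The last column is for the RDQ score scale and holds whatever margin is set. The power column restates the plan's own calculation, which is for detecting a difference; it is not the power of the non-inferiority test.

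More surveys do not solve this, because the SE cannot fall below 1.3 × √(2 × ICC). Above ICC = 0.42²/[2 × 1.69 × (2.576 + 1.282)²] ≈ 0.0035, no number of surveys in one VISN per arm reaches 90% power for 0.42.

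**Baseline adjustment.** Assume a correlation of 0.5 between baseline and 3-month RDQ, and suppose the adjustment fully removes a stable VISN difference. Let s be the share of total variance due to VISN-by-time variation that remains. Then SE = √{2 × 1.69 × [s + 0.75 × (1 − s)/287]}.

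| s (assumed) | SE | Power for 0.42 |
|---|---|---|
| 0 | 0.094 | 97% |
| 0.001 | 0.110 | 89% |
| 0.01 | 0.206 | 29% |

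The unadjusted figures are therefore not bounds. Two VISNs cannot show which row applies.

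**The case against.** **Baseline RDQ, the longitudinal model and the matched control VISN may remove most of the VISN difference.** This stands in part. A stable difference may be removed, and the 97% row shows the favourable case. But neither repeated measures nor a comparable control VISN provides a VISN-level error term for change over time, and the matching criteria are not stated.

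**The power figures describe the wrong test.** This is fair as a caution. H3 is judged with a 90% CI against a margin that is not given. If the margin were assumed to be 0.42 and the true difference zero, Φ(0.42/SE − 1.645) gives about 99%, 96% and 63% at ICC 0, 0.001 and 0.01. A smaller margin would give less. The inflated error rates do not depend on the margin.

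**The size rests on assumed ICCs.** It does. The structural point and the reproduction of 287 do not.

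**Other evidence exists.** Visits, endoscopy and admissions for upper GI conditions come from electronic records and are not limited to two VISNs. They are useful partial evidence, but section 7.2.2 notes that over-the-counter medication and non-VA care fall outside VA data. They do not repair the H3 interval.

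**H3 is secondary and the two-VISN restriction is disclosed.** Both are true. Disclosure does not make the specified model estimable, and the H3 hypothesis is still worded as intervention against control.

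Choosing the intervention VISN on Dashboard activity, which is known only after randomization, limits generalisability. It does not clearly favour the programme, since greater exposure may make non-inferiority harder to show.

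**Conclusion.** The concern holds and must be fixed. The VISN-clustering and strata terms specified for H3 cannot be estimated with one VISN per arm, and the H3 sample size is correct only if there is no between-VISN variation. Both conclusions follow from the documents alone.

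The size of the consequence is illustrative. At an assumed RDQ ICC of 0.001 to 0.01, a nominal 5% one-sided error would be about 7% to 20% if VISN is ignored, and the 90% half-width would need to be 0.20 to 0.35 instead of 0.18. Baseline adjustment could make this much better or leave it nearly as bad, and the data cannot show which. A programme-level non-inferiority conclusion on symptoms is therefore not supported. The problem is confined to H3.

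**What to change.** 1. **Section 8.1.2:** state that the 90% power assumes independent patients and no between-VISN variation. Do not add a power range from assumed ICCs, since the documents have no RDQ value to anchor one.
2. **Section 8.3:** give H3 its own model without VISN and strata terms, adjusted for baseline RDQ and reconciled with the longitudinal model in section 6.3. State the scale, because section 8.1.2 treats RDQ as continuous while section 8.3 uses a logit link. Add facility clustering if there are enough facilities (the number is not given); this captures variation within a VISN, not between VISNs. State that the CI excludes between-VISN variation.
3. **Reporting:** present H3 as a comparison of two selected VISNs, say how they were selected, and draw no programme-level non-inferiority conclusion. Leave H1 and H2 unchanged.

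The cost is one refit of the H3 model and changes of wording in the SAP and report, with no new data. The price is a more limited claim about symptoms.
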